### Study Procedures/Research

**Study Procedures:** Participants will flow through the study in the following manner:

1. *Consent and Initial Screening Visit (V0):* Site study personnel will discuss study goals, activities, and requirements with the parent/legal guardian and/or potential participant; complete the informed consent discussion, and if/when appropriate the potential participant will complete assent/consent to join study. Following assent/consent, site

study personnel will perform diagnostic assessments and interviews and assess inclusion/exclusion to determine if the participant is eligible for enrollment.

Duration: ~2-3 hours remotely or in-person.

2. *Baseline Assessment (V1)*: Following enrollment, the participant will perform all social/cognitive baseline characterization assessments and questionnaires prior to the intervention period. Duration: ~2 hours remotely or in-person.
3. *Randomization*: Participants will be randomized into one of three treatment arms.
4. *Digital device Set-Up and Proctored Application Use (V2)*: The participant will be oriented to the intervention activities and program application(s). Participants will also complete a series of digital assessments during this visit via BrainHQ. Participants with a compatible personal device that are willing to download the necessary application(s) for program use will have their device set-up at this visit and will be guided to schedule reminders for completing their study activities. Participants that do not have a compatible personal device, do not wish to use their personal device, or do not agree to configure their settings and download the necessary application(s) for program use will be loaned a digital device for the duration of the *Intervention and Program Use* period. Participants will be asked to sign a form acknowledging they have been loaned a study device. The study team will attempt to complete this visit on the same day as V1, but a separate visit may be scheduled, if necessary. Duration: ~30-60 minutes remotely or in-person.

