### ***Cognitive Function***

At *Screening Visit (V0)*: Cognitive status will be determined using the WASI-II or a comparable measure in their medical/clinical records. An IQ > 70 is required to enroll in the study. Adult participants will undergo an additional cognitive assessment, the UBACC. Participants must score within the normal range; participants who cannot pass the UBACC will not be eligible for enrollment.

For *Baseline (V1)*, *Mid-Intervention (V3)* and *Post-Intervention (V4)* Visits: We will assess cognition directly by administering the Behavior Rating Inventory of Executive Function, Second Edition (BRIEF-2), Mind Bender, and PsyToolkit's Eriksen Flanker and Wisconsin Card Sorting Tasks.

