### ***Intervention Embedded Assessments***

All participants, regardless of treatment group, will complete the ten sensory processing assessments before and after the first intervention period.

**The primary outcome** measures, including digital assessment completion rate, NB-SCT program adherence, usability ratings, reported adverse effects, and overall program completion rate will be used to assess feasibility, acceptability and usability of CICADAS app.

**Secondary outcomes** measures include baseline, mid-intervention, and post-intervention assessments as well as the weekly number of initiated or reciprocated social gatherings related to or in addition to PEERS assigned social activities.

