### Treatment Interventions

**CICADAS app:** Participants will complete sensory processing assessments and neuroplasticity-based social cognitive training (NB-SCT) exercises on a digital device for a total of 40 hours through BrainHQ. The CICADAS app captures user-specific sensory processing abnormalities (SPA) through 10 brief computerized assessments. Participants will complete these sensory processing assessments before and after the first intervention period. The data from these assessments guide and personalize the delivery of 13 NB-SCT exercises. The NB-SCT exercises are adaptive with the task difficulty adjusting on a trial-to-trial and session-by-session basis to the abilities of each individual. Participants will need to log in to access these assessments and exercises using a study provided username that contains no personally identifiable information.

| CICADAS Assessments and Training Exercises |                                      |  |                   |
|--|--------------------------------------|--|-------------------|
| Sensory Processing Assessments      |                                      | Neuroplasticity-based Social Cognitive Training Exercises |                   |
| Sound Sweeps                               | Auditory Perception/Processing Speed | That Emotion   | Go/no-go task*    |
| Beep Seeker                                | Auditory Distractor Suppression      | Stop Signal  | Stop-signal task* |

|   |                                      |                       |                              |
|---|--------------------------------------|-----------------------|------------------------------|
| Fine Tuning   | Auditory Distractor Suppression      | Rule Switch           | Set switching task*          |
| Visual Sweeps   | Visual Perception/Processing Speed   | Emotional Faces       | Stroop-like task*            |
| Bubble Pop  | Visual Multiple Object Tracking      | Emotion Tracker       | N-back task*                 |
| Mind Bender   | Visual Task Switching                | Letter Identification | Dot probe task*              |
| Tap The Emotion   | Emotion Detection/Inhibitory Control | Say What?             | Prosody theory of mind task  |
| In the Know   | Auditory Social Memory               | Voice Choice          | Prosody naming task          |
| Face to Face  | Emotion Match/Identification         | Face Replay           | Emotional memory task        |

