## Blinding

Un-blinded Roles: PEERS clinicians and the site study coordinator are un-blinded in order to lead group sessions and support for participants using their assigned programs. They will be distinct from staff administering and scoring assessments. Additionally, designated personnel that are un-blinded may not participate in the assessment and evaluation at Mid-Intervention (V3) or Post-Intervention (V4) assessment visits of study participants.

Blinded Roles: All site staff responsible for the administration and scoring of participant assessments visits conducted after randomization will remain blinded to participant treatment. The Site Principal Investigator will be required to complete a Delegation of Authority Form, indicating which activities individual research team members will be authorized to complete. Principal Investigators will also remain blinded.

Depending upon the extent to which they are responsible for data collection and/or entry, *site study coordinators* may or may not remain un-blinded to participant treatment. This will be clarified on a site-by-site basis and will be noted on the Site Principal Investigator Delegation of Authority Form.

To prevent un-blinding, the following will occur:

1. The treatment arms will be identified as “Arm A, Arm B, and Arm C.”

2. Participants will be reminded not to discuss details related to treatment with blinded psychometricians and/or clinical evaluators during the informed consent process as well as prior to initiation, and at the conclusion of, each assessment visit;
3. Site study personnel will be instructed to not discuss details of either treatment arm during open participant groups or forums outside of the assigned group sessions or cohort discussions;
4. Site study personnel will be required execute the protocol in a manner that minimizes the possibility of accidental un-blinding of psychometricians or clinical evaluators (e.g. unintended viewing of treatment sessions);

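### The 'before' values for the digital sensory tests are, in the listed visit order, taken after randomisation at the visit that introduces the assigned intervention, and blinding at that visit is not specified

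*Protocol*

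**What the plan says.** The protocol's Study Procedures/Research section numbers the steps. Step 2 is the V1 baseline. Step 3 reads "Participants will be randomized into one of three treatment arms". Step 4 is V2, at which the device is set up and the participant is introduced to the intervention and the app. The same step adds: "Participants will also complete a series of digital assessments during this visit via BrainHQ". On timing it says "The study team will attempt to complete this visit on the same day as V1", but a separate visit is allowed.

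The section on Intervention Embedded Assessments states: "All participants, regardless of treatment group, will complete the ten sensory processing assessments before and after the first intervention period". Treatment Interventions describes the tests: "The CICADAS app captures user-specific sensory processing abnormalities (SPA) through 10 brief computerized assessments". It also says that the app runs through BrainHQ.

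On staff, the Blinding section states: "All site staff responsible for the administration and scoring of participant assessments visits conducted after randomization will remain blinded to participant treatment". It also lists the site study coordinator as un-blinded in order to support use of the assigned programs, and it bars un-blinded staff by name from V3 and V4. V2 is not named. Appendix I has no V2 column and does not list the ten tests as a set.

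**The concern.** A baseline is safe in a randomised comparison because assignment cannot have influenced it. A 'before' score taken after assignment loses that protection. At V2 the participant is being introduced to the assigned intervention, and someone is there to guide app use. If testing comes after that introduction, an adolescent in Arm A may know that PEERS is delayed. The Sample Size Justification says the target sample is adolescents already seeking PEERS, so an effect on effort is plausible. An un-blinded proctor could also influence performance, in either direction.

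At stake is the between-arm comparison of change in the digital sensory scores. The SAP's linear mixed model takes the group-by-time interaction as the key result, so a shift in one arm's first measurement passes straight into that estimate.

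**Working it through.** **1. Are the V2 tests the ten?** The ten are computerised, are delivered through BrainHQ and are required before the first intervention period. V2 is the only pre-intervention visit at which a BrainHQ assessment series is described. The identification is therefore well supported, but it is an inference. One exception is explicit: Mind Bender is among the ten in the Treatment Interventions table, and the Cognitive Function section also schedules it at V1, V3 and V4 ("Mind Bender, and PsyToolkit's Eriksen Flanker and Wisconsin Card Sorting Tasks"). That test has a pre-randomisation value.

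**2. Is V2 after assignment?** Yes, in the listed order: V1, randomisation, V2. Same-day scheduling does not change the order.

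**3. Is V2 blinded?** Not specified. The general rule would reach V2 if V2 counts as an assessment visit. The explicit bar names only V3 and V4. No section says who proctors V2 or whether testing precedes orientation.

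**4. Which analyses use the scores?**

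| Analysis | Exposed? | Reason |
|---|---|---|
| Primary digital-assessment outcome | No | It is a completion rate |
| SCAN-3:A and BBCSS | No | Given at V1, before randomisation |
| SAP hypothesis (b), A1-A3 | No | The ten are given only before and after the first period, so there is no week-32 value |
| SAP hypothesis (c), B2-B3 | No | Same reason |
| SAP composites | Not through the ten as a set | The set is in none of them |
| Digital scores in A1-A2, B1-B2 and C1-C2, including hypothesis (a) | Yes | The first value is post-assignment |

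**5. Size, by illustration.** The plan gives no figure to reproduce. From the documents: 16 completers per arm (General Study Design) and p < 0.05 (SAP). Assumed: a shift of 0.2 to 0.3 SD in one arm's 'before' score, equal SDs at both times, correlation rho between them, a two-sided test and the normal approximation.

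A shift d in one arm's first value changes the between-arm difference in change by d. The standard error of that difference, in SD units, is

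SE = sqrt(2(1 - rho)) x sqrt(2/16).

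With s = d/SE and Phi the standard normal distribution function, the false-positive rate when there is no true difference is Phi(s - 1.96) + Phi(-s - 1.96).

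| rho | SE | 0.2/SE | 0.3/SE | False-positive rate |
|---|---|---|---|---|
| 0.3 | 0.418 | 0.48 | 0.72 | 7.7% to 11.1% |
| 0.5 | 0.354 | 0.57 | 0.85 | 8.7% to 13.6% |
| 0.7 | 0.274 | 0.73 | 1.10 | 11.3% to 19.5% |

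Adjusting for the shifted score as a covariate would shrink the bias to rho x d but not remove it: 0.06 to 0.09 SD at 0.3, 0.10 to 0.15 SD at 0.5 and 0.14 to 0.21 SD at 0.7.

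**The case against.** The strongest reply is that little depends on these scores. Under Sensory Processing, the protocol names SCAN-3:A and BBCSS, both measured at V1. A reader might infer that the sensory outcome in SAP hypotheses (a) to (c) has no pre-randomisation baseline; the documents do not support that. This part of the reply stands, and it limits the point to the digital scores over the first 16 weeks.

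A reader might also infer that V2 lies outside the blind, or that staff cannot obey both the orientation step and the blinding rule. Neither is shown. V2 may not count as an assessment visit. If it does, one person could orient and a different, blinded person could test, and the Blinding section does require un-blinded staff to be distinct from those who assess. The accurate statement is that blinding at V2 is unspecified.

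The mechanism is also narrow. The two apps are meant to look alike, and Arms B and C both start PEERS at once, so disappointment over a delay does not touch B versus C. A lowered first score in Arm A would inflate Arm A's gain, which works against hypothesis (a). This stands for that mechanism. It does not settle the direction of a proctor effect, and a bias against the hypothesis still misstates an estimate meant to help power the next trial.

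Loss of participants between randomisation and V2 adds little, because the SAP's primary population requires attendance at one PEERS session.

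Finally, the tests are computerised, and the SAP concedes that it lacks power for an augmentation effect. Both lower the stakes. Neither is a reason to keep an order that can be changed at little cost.

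**Conclusion.** The point holds in limited form. Followed as written, the plan yields a post-assignment 'before' value for the digital sensory tests (Mind Bender also has a V1 value), with the proctor's role and the order of testing and orientation left open. This exposes exploratory between-arm comparisons of first-period change in those scores, chiefly A versus B and A versus C.

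No document supports any particular shift. If one arm moved by 0.2 to 0.3 SD, the bias would be about 0.5 to 1.1 standard errors across correlations of 0.3 to 0.7. The conclusion also rests on reading the unnamed V2 series as the ten tests. It should be corrected because prevention is cheap and the bias cannot be fully removed afterwards; it does not threaten the primary feasibility results.

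**What to change.** Complete the ten digital tests before randomisation. Either of two routes works:

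- give them at the end of V1, on a site device or the participant's own; or
- move step 3 so that randomisation follows device set-up and the digital tests but precedes orientation to the assigned app.

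The choice matters because devices are at present set up or loaned only at V2. In either case, state under Intervention Embedded Assessments that 'before' means before randomisation, name the ten tests as the BrainHQ series, and add them to Appendix I. The SAP should also name the measure behind its sensory-symptom strata: if it is these tests, they must precede randomisation in any case.

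Cost: a protocol edit, a slightly longer pre-randomisation session (V1 is already about 2 hours, and the protocol notes that assessments can be tiring), some device logistics, and a few people tested who are never randomised. No test is added, and no visit either, since V1 and V2 are already intended for the same day.

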## General Study Design

We will employ a three-arm, active-controlled, randomized crossover trial to assess the safety and efficacy of CICADAS app in adolescents with ASD, and to evaluate its potential as a stand-alone treatment, as a primer for PEERS, or as a treatment enhancer of PEERS. We will randomize adolescents with ASD (ages 11-18) to CICADAS only, PEERS + CICADAS app, or PEERS + Active Control app.

Approximately 56 participants will be consented to ensure the successful completion of 48 participants (16 participants per treatment arm). A diagnostic interview will be performed to determine eligibility. Following inclusion and enrollment, participants will complete a set of assessments prior to the intervention to establish their baseline performance. Participants will then be randomized to the CICADAS only group (Arm A), PEERS + CICADAS app group (Arm B), or PEERS + Active Control app group (Arm C) and spend up to 16 weeks engaged in their assigned intervention. After 16 weeks, a full battery of assessments will be administered. For the next 16 weeks, Arm A will continue with PEERS only and Arms B and C will receive no treatment during this period. At the end of the intervention period, a full battery of assessments will be administered a second time to evaluate changes in performance. Finally, participants will be asked to fill out an online exit survey to rate enjoyment, usability, perceived benefits, and ease of fit into schedule.

During the first intervention period, participants assigned to the CICADAS only will complete NB-SCT exercises for 16 weeks. Participants assigned to PEERS + CICADAS will engage with the CICADAS app and complete weekly 1-hour PEERS group sessions for 16 weeks. Participants assigned to receive the PEERS + Active Control will engage in the Active Control app and complete weekly 1-hour PEERS group sessions for 16 weeks. During the second intervention period, participants assigned to receive PEERS only will complete weekly 1-hour PEERS group sessions for 16 weeks. During both intervention periods, these participants may have weekly electronic check-ins with site study personnel (as needed). The CICADAS app and the Active Control app icons, design and user experience will look the same as to not unblind the participants.

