Participants expressing interest in returning their device to its original settings will be instructed by site study personnel on how to delete study application(s) during this visit or at the time of study exit. Participants loaned a study device will be asked to return the loaned device at this visit. If participants were loaned a digital device to complete study activities at home and no longer wish to participate in study activities, including their post-intervention interview, site study personnel will attempt to coordinate with the participant to return the device at a time that is convenient for the participant. If the participant cannot be reached, site study personnel will send them a letter asking them to return the device along with a box with a return label. Participants will be invited to come back for a follow up visit in this letter, but also reminded that they are free to no longer participate in the study. Site study personnel may also send this letter to participants who completed all study activities but forgot to return the device and are unable to coordinate with site study personnel to return it.

9. *Exit Survey* (~10 minutes): Participants will be asked to fill out an online exit survey to rate enjoyment, usability, perceived benefits, and ease of fit into schedule.

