### Treatment Arms

**Arm A:** Participants assigned to Arm A will engage in CICADAS only for the first 16 weeks of the intervention period. After the completion of the first intervention period and the mid-intervention assessment (V3) visit, these participants will then be assigned to the PEERS only group for the second 16 weeks of the intervention period.

**Arm B:** Participants assigned to Arm B will engage in PEERS + CICADAS for the first 16 weeks of the intervention period. After the completion of the first intervention period and the mid-intervention assessment (V3) visit, these participants will then be assigned to No-Contact (no active intervention) for the second 16 weeks of the intervention period.

**Arm C:** Participants assigned to Arm C will engage in PEERS + Active Control for the first 16 weeks of the intervention period. After the completion of the first intervention period and the mid-intervention assessment (V3) visit, these participants will then be assigned to No-Contact (no active intervention) for the second 16 weeks of the intervention period.

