### Primary Outcome - Feasibility

Efforts will be made to assess all participants who have completed the minimum required intervention activities: For Arm A (CICADAS only), completing at least 1 hour of NB-SCT; for Arm B (PEERS + CICADAS), completing at least one PEERS group session and 1 hour of NB-SCT; and for Arm C (PEERS + Active Control), completing at least one PEERS group session and 1 hour of games.

As the main goal of this Phase I trial is to evaluate the feasibility, acceptability and usability of the CICADAS app, we will conduct an analysis of the following primary outcome measures in all ITT-CU participants:

1. Digital assessments completion rate. We expect that  $\geq 80\%$  of participants will complete the digital assessment battery at least twice during the CICADAS intervention;
2. NB-SCT program adherence, that is automatically tracked on the back-end data portal (percentage of training sessions completed). Based on our previous studies (CLIMB, MOODIFY, WASABI) and pilot, we expect that  $\geq 70\%$  of participants will complete 20 hours of NB-SCT;
4. Reported side effects (raw score). Based on our previous findings, we expect 0 adverse events due to program use;

5. Overall program completion rate. Based on previous findings from CLIMB and from the pilot in ASD, we hypothesize full program completion in  $\geq 70\%$  study participants.

Secondary Outcome - Preliminary Efficacy

The secondary outcome measures will be collected by trained personnel blind to treatment assignment at baseline, half-way through the intervention, and immediately after the treatment for all randomized participants. Weekly measures will capture the number of initiated or reciprocated social gatherings related to or in addition to PEERS assigned social activities.

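### Usability is a primary outcome, but the only rating named for the randomised trial is an exit survey about 16 weeks after app use ends

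*Protocol*

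**What the plan says.** Protocol, Intervention Embedded Assessments, lists the primary measures as "including digital assessment completion rate, NB-SCT program adherence, usability ratings, reported adverse effects, and overall program completion rate". The SAP (Primary Outcome - Feasibility) also names usability in the main goal of the trial.

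The usability rating is described in two places, both at the end of the study. General Study Design, after the second full battery, says: "Finally, participants will be asked to fill out an online exit survey to rate enjoyment, usability, perceived benefits, and ease of fit into schedule". Study Procedures/Research makes it step 9, after the V4 visit in step 8: "Participants will be asked to fill out an online exit survey to rate enjoyment, usability, perceived benefits, and ease of fit into schedule". Appendix I has no usability row at V1, V3 or V4, only a study-exit line to be completed as needed.

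Under Treatment Arms, Arm A "will engage in CICADAS only for the first 16 weeks of the intervention period" and then moves to PEERS only. Arm B "will engage in PEERS + CICADAS for the first 16 weeks of the intervention period" and then has no active intervention. Arm C uses its control app over the same 16 weeks.

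SAP, Evaluation Time Points, states in one general line each that primary and secondary measures are collected at weeks 0, 16 and 32. The SAP's numbered list of primary measures runs 1, 2, 4, 5.

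For withdrawals, Withdrawal from the Protocol provides an informational interview about reasons, conduct issues and adverse events. It mentions no usability rating.

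**The concern.** A usability rating is most informative while the user still remembers the product. Followed as written, the protocol asks for it a full intervention period after the app was last opened, and what happened in between differs by arm: PEERS in Arm A, nothing in Arm B. The survey also covers enjoyment and perceived benefit without saying whether the app, PEERS or the whole study is being rated. PEERS is part of the experience in both CICADAS arms by then, concurrently in Arm B and afterwards in Arm A, so answers about the app cannot be cleanly separated.

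The late timing also leaves a further 16 weeks in which participants can be lost before they rate anything. At stake is one of five primary measures in a trial meant to prepare a larger efficacy study and a device submission.

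**Working it through.** **1. Timing.** Inputs: end of app use at week 16 (Treatment Arms; Study Procedures, steps 5 and 7); exit survey after V4 at about week 32 (Study Procedures, steps 8 and 9).

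- Lag as written: 32 - 16 = 16 weeks. This is nominal, because paused PEERS sessions can lengthen a period.
- Lag if rated at V3: 16 - 16 = 0 weeks.

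The SAP's Statistical Plan has Arm A, like the others, without contact in the second period, while the protocol gives Arm A PEERS. Those passages need reconciling, but the lag is 16 weeks on either reading.

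**2. Does the SAP's week-16 line supply an earlier rating?** It says the same of week 0, when nobody has used the app, so it cannot be read literally as a usability schedule. No week-16 usability instrument appears in the protocol's procedures or in Appendix I. The two documents are therefore inconsistent.

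**3. The plan's own figure.** Sample Size Justification recruits 56 to obtain 48 completers at 15% non-completion.

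- 48 / (1 - 0.15) = 56.5; 48 × 1.15 = 55.2; 56 × 0.85 = 47.6. The stated 56 is reproduced to within rounding, and the sample size is not in dispute.

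**4. Participants without a rating.** CICADAS is used in two of three equal arms.

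| Base | CICADAS arms | 15% lost | Rated |
|---|---|---|---|
| 48 randomised (SAP, Statistical Plan) | 48 × 2/3 = 32 | 0.15 × 32 = 4.8, about 5 | 27 |
| 56 recruited (protocol) | 56 × 2/3 = 37.3, about 37 | 0.15 × 37 = 5.6, about 6 | 31 |

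This assumes that every non-completer gives no rating.

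**5. What the missing ratings could do (illustration).** Assume 80% of raters are favourable; this figure is not in the documents.

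- Base 37: raters favourable 0.80 × 31 = 24.8. If no leaver is favourable, 24.8 / 37 = 67%; if all are, (24.8 + 6) / 37 = 83%.
- Base 32: 0.80 × 27 = 21.6. The limits are 21.6 / 32 = 68% and (21.6 + 5) / 32 = 83%.

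The range is two-sided. It spans the 70% and 80% levels that the SAP sets for other primary measures. Recall error would come on top and cannot be quantified from the documents.

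**The case against.** The strongest reply is that the documents leave room for an earlier rating. The SAP says primary measures are collected at week 16. Appendix I is weak evidence of absence, since it also omits the ten digital assessments that the protocol places before and after the first period. Its study-exit line could cover a survey at withdrawal. This stands in part: an earlier rating is not ruled out. But none is specified, and the only timing given is after V4.

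Four stronger readings are tempting, and the documents do not support them.

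- *The SAP has no usability analysis.* The list skips number 3, exactly where usability falls in the protocol's order. The entry may have been lost when the text was extracted, so the omission is not established.
- *The result will be biased upward.* Sample Size Justification reports that several earlier participants stopped because of aversion to auditory stimuli, with 73.2% completing visual and 38.5% auditory training, so upward bias is plausible. But the same section ascribes the high dropout to design issues. The protocol also lets people stop using the app and still attend V3 or V4, provided they meet the minimum number of sessions, so dissatisfied users may still reach the survey.
- *PEERS contaminates one arm only.* Arm B receives it with the app, so moving the survey to V3 does not by itself separate the two there.
- *The whole feasibility conclusion rests on recalled ratings.* Adherence is tracked automatically, and digital-assessment and programme completion are also primary.

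**Conclusion.** The timing point holds. Followed as written, a primary outcome is measured about 16 weeks after exposure to the app ends, by an instrument that does not name what is being rated, with no stated rating for early leavers. The SAP's general week-16 statement does not cure this and conflicts with the protocol's procedure.

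At the projected 15% loss, about 5 to 6 of 32 to 37 CICADAS participants would be unrated. That rests on equal allocation and on non-completers receiving no survey. The direction and size of any distortion are not known. Whether the SAP defines a usability analysis cannot be settled from the available text.

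**What to change.** 1. Give the same 10-minute online survey at V3 in all three arms, and at withdrawal to anyone leaving before V3. Word it to ask about the assigned app, separately from PEERS.
2. Use that rating as the primary usability measure, with Arm C as reference. Keep the week-32 survey for overall study experience.
3. Add the V3 row to Appendix I, and make the SAP's Evaluation Time Points agree with the protocol on when usability is rated.
4. Confirm or restore item 3 of the SAP's primary list with definition, threshold, timing and population. The population needs care: the CICADAS-users set is described as those who received CICADAS with PEERS, which leaves Arm A's place unclear.

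The cost is a minor protocol amendment, one SAP item and one short online form. Sample size, arms and treatment are unchanged. The downside is slight added burden at V3. Because V3 assessors are blinded, the form should be completed online and kept from their view.
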